### **Focus and study population**

As described, we have consulted widely with people with inflammatory arthritis, rheumatology, palliative care, primary and community healthcare professionals. They confirmed this is an important topic to investigate. They encouraged us to explore the potential value of Supportive Care, in addition to Palliative Care, as although not widely available outside of cancer services, the similarities in personal health and emotional challenges for Rheumatology patients may mean it is highly appropriate.

This study focuses on four common types of inflammatory arthritis:

- Rheumatoid Arthritis (RA)
- Psoriatic Arthritis (PsA)
- Juvenile Idiopathic Arthritis (JIA)
- Axial Spondyloarthritis (axSpa)

These conditions often involve similar symptoms, treatments, and related health issues. While there are other rare, life-threatening rheumatic diseases, this study concentrates on the more common ones to better understand how Supportive and Palliative Care could help throughout a person's life.

## **2 THEORETICAL FRAMEWORK**

This project comprises three discrete and iterative work-packages (WP). Qualitative methods have been selected for work-package 1 (WP1) which explores with people living with an inflammatory arthritis, what their understanding and perspectives are of PSC, and how PSC may support them to live well. Semi-structured interviews are the optimal method to explore a topic where little prior knowledge exists, and in the context of the lived experience. Semi-structured interviews allow for core topics to be raised for discussion but give scope for participants to raise unanticipated issues; the use of a topic guide facilitates the discussion but the precise wording and order of questions is contextual and responsive to the participant's account.

Work-package 2 (WP2) aims to explore (1) Rheumatology, General Practice and Community healthcare professionals' (HCP) views on PSC, and (2) Palliative Care HCPs' views on Inflammatory Arthritis and Supportive Care, how they currently collaborate, and how PSC may help people with Inflammatory arthritis to live well. As this work seeks to capture a large volume of data from a range of different populations at a single time point, then a survey format is appropriate. The majority of the survey data will be quantitative to ensure forced choice responses for clarity of data, and ease of data analysis.

The final work-package (WP3) will take a qualitative approach as it aims to explore the views of stakeholders, where no prior expectations have been set. Focus groups provide an opportunity for exploration of a topic, facilitated by a topic guide, to elicit the range of opinions and recommendations within the group. They can also enable group consensus on a topic where this is required.

### **3 STUDY AIMS, OBJECTIVES, RESEARCH QUESTIONS & OUTCOMES**

#### **3.1 Aims:**

- To explore the potential role of PSC for people with inflammatory arthritis.
- Describe any unmet patient need.
- Develop clinical and research recommendations to help people with inflammatory arthritis to live well over the course of their disease.

#### **3.2 Objectives**

- Create 3 short videos for use within our WPs, to aid understanding and ensure consistent messaging in our project.
- Conduct semi-structured online or telephone interviews with people living with an inflammatory arthritis to understand their views of PSC, and how PSC may support them to live well throughout the course of their disease (WP1).
- Conduct an e-survey with healthcare professionals working in Rheumatology, Palliative Care, Primary Care and Community services to determine current provision of PSC for people with inflammatory arthritis and understand views about the potential value of PSC support (WP2).
- In collaboration with Public Contributors, assimilate data from WPs1 and 2 into a 'key findings' summary document and presentation, to be shared with expert stakeholders. Repeat previous rapid literature review and include any new findings in the summary document and presentation (WP3).
- Conduct four online stakeholder focus groups to agree: a) the nature and scope of 'unmet need' as described in our data; b) recommendations for future clinical practice and research, and patient identified areas of importance, which should be measured.
- Disseminate study findings.

### 3.3 Research questions:

1. What are the views of people with inflammatory arthritis of PSC and how PSC may support them to live well?
2. How do Rheumatology, PC, Primary Care and Community services healthcare professionals currently collaborate, and what do they perceive as the potential future value of PSC to support people with inflammatory arthritis to live well?
3. What is the nature/scope of patients' unmet need?
4. What are expert stakeholders' recommendations for future clinical practice and research to help people live well with inflammatory arthritis via PSC throughout the disease course?

### 3.4 Outcomes

The primary outcomes for this research will be:

- A description of the nature and scope of unmet patient need,
- Clinical and research recommendations, informed by expert opinion and the 'six pillars' framework of the British Society of Lifestyle Medicine, which describe the potential role of PSC for people with inflammatory arthritis throughout the disease course. We will particularly consider Supportive Care, within the 'six pillars' framework, as this includes improving a person's general physical and mental health. These recommendations will be shared with people with inflammatory arthritis, clinicians, academics and service commissioners. Future work will explore how to implement the recommendations into practice to improve the lives of people with inflammatory arthritis.
- Patient identified areas of importance which should be measured in future work.

## 4 STUDY DESIGN /SAMPLE/ METHODS/ ANALYSIS

### 4.1 Overview of study

This exploratory study comprises three sequential work-packages (WP1-3), which build on each other and include qualitative and quantitative data collection.

### 4.2 WP1 (months 4-9)

**Explore with people living with an Inflammatory arthritis, what their understanding and perspectives are of Palliative and Supportive Care, and how Palliative and Supportive Care may support them to live well.**

#### 4.2.1 Inclusion and exclusion criteria

**Inclusion criteria:** Adults (> 18 years) with a diagnosis of arthritis (Rheumatoid, Psoriatic or Juvenile Idiopathic) or Axial Spondyloarthritis; able to understand and communicate in verbal and written English (or via an interpreter nominated by the participant or provided via an agency by the research team); in receipt, or not in receipt of Palliative Care services; access to Microsoft Teams or a telephone; and consent to sharing preferred contact details. **Exclusion criteria:** Cognitive

impairment that impedes communication; non-English speaker (should an interpreter not be available).

**4.2.2 Sample size:** 20 to 30 participants will be sought. 15-30 participants is considered sufficient to capture rich, focused data, and to identify patterns or tendencies.

**4.2.3 Patient recruitment** will purposefully seek an adult heterogeneous sample (range of ages, in receipt or not of palliative care, and from across the disease course) from Bath and Bristol Rheumatology clinics; Bristol Bone and Joint Health Integration Team; Bath Institute for Rheumatic Diseases; Dorothy House Hospice and wider national hospice network who have agreed to be Participant Identification Centres (PIC) sites. As an NIHR portfolio study, an advertisement will be shared via NIHR networks e.g. RDN Residential Settings Network and NIHR Be Part of Research. Advertising via social media platforms (e.g. Facebook, 'X', LinkedIn) will be considered dependent on response in the previous groups. We will seek to include diverse representation by working with organisations who serve ethnically diverse communities e.g. Sawubona (We See You) and Bath and Bristol Research Engagement Networks. Potential participants will not be approached directly by the research team ensuring participation is entirely voluntary and self-selecting.

An interpreter will be engaged via an agency for those people who do not speak English at a fluency which would enable them to participate. On expression of interest, the relevant study documents will be translated (e.g. Participant Information Sheet, consent form, data privacy notice and video). We cannot guarantee an interpreter will be available for all languages, and this may impact recruitment.

**4.2.4 Recruitment materials** will be co-designed with Public Contributors and include contact details (email, telephone) of the Research Fellow (RF) for more information. On receipt of an expression of interest, the RF will email or telephone to confirm eligibility and share the Participant Information Sheet, consent form, and data privacy notice via email or post. Communications and documentation will be translated where applicable. The RF will email or telephone to follow-up and will arrange an agreed interview date. Only two attempts to contact will be made at each time point.

**4.2.5 Data collection** will be via semi-structured individual interviews conducted online via Microsoft Teams. Guidance on Microsoft Teams will be provided as needed. Communication via MS Teams can be via computer or telephone (without the need for a camera). Our participant information documents will recommend conducting the interview in a private area, or at a time when privacy can be provided, and the researcher will offer flexibility in appointment times. An interpreter will be provided for the duration of the interview, if required and available.

A topic guide will be co-designed with Public Contributors and informed from: existing literature, research objectives, and pre-application focus group feedback from people with Inflammatory arthritis. An embedded pilot of the interview schedule will be conducted with two participants.

Following provision of responses to any questions about the study and receipt of **verbal participant consent**, interviews will be recorded using an embedded audio recording function or via Dictaphone if any technical challenges are encountered. Participants will be asked for their understanding and perspectives on PSC before being shown a brief video describing PSC and the support these services can offer. Subsequent questions will explore if the video has changed participants' views, which circumstances Palliative and/or Supportive Care may have been helpful to the participant in the past, or envisaged future benefit. As the topic area has potential to cause distress, an a priori distress protocol for interviews will guide the RF's response and actions throughout the interview (see supporting documents).

Limited personal data will be collected during the interviews (age, sex, ethnicity and geographical location), for the purposes of describing the sample in dissemination activities and to assist with efforts to ensure inclusion as per NIHR INCLUDE guidelines.

Data will be transcribed verbatim using the transcribe function within Microsoft 365, checked for accuracy by the RF, and thematically analysed following Braun and Clarke. Transcripts will be pseudonymised via usage of unique ID numbers. No participant will be identifiable from any reports or dissemination activities undertaken.

Participants' contact details will be retained if they wish to receive a summary of study findings or contribute to stakeholder focus groups (WP3).

#### **4.3 WP2 (months 8-12)**

**Explore Rheumatology, General practice and Community healthcare professionals' (HCP) views on Palliative and Supportive Care, and Palliative Care HCPs' views on Inflammatory Arthritis and Supportive Care, and how Palliative Care and Supportive Care may help people with Inflammatory arthritis to live well.**

##### **4.3.1 Inclusion and exclusion criteria**

**Inclusion criteria:** Registered HCPs working in Rheumatology; registered and non-registered HCPs in Palliative Care; Primary Care (GPs); Community teams (district nurses, therapists). Non-registered staff are key personnel in Palliative Care.

**Exclusion criteria:** Living and working outside UK.

**4.3.2 Sample size:** As this is an exploratory study, sample size calculations are not necessary. We aim to recruit a minimum of 50 participants to draw meaningful preliminary conclusions.

**4.3.3 Recruitment:** As a Research Delivery Network (RDN) Portfolio study, recruitment to the e-survey will be via the RDN. Additional advertising will be via an e-link to the survey on professional organisational networks, websites, and social media platforms (e.g. Facebook, 'X', LinkedIn).

**4.3.4 Data collection** will be via e-survey using the Qualtrics platform, to determine current provision, and understanding of the value, and potential value of PSC for people with an Inflammatory arthritis. Survey items will be informed by WP1 data, and Speciality expertise within the research project team, and piloted with five HCPs

prior to being finalised. The survey platform will include the participant information sheet and informed **consent** prior to presentation of open and closed questions to collect data including clinical role, level of education, experience since qualification, experience in current specialty, personal experience (self or close relative) and geographical location. It will comprise multiple-choice and Likert scale items with limited open-text options about participants' understanding of PSC (Rheumatology, Primary Care and Community professionals), or Inflammatory arthritis and Supportive Care (Palliative Care professionals), and participants' current practice. Videos will be embedded in the survey about PSC services or Inflammatory arthritis, as appropriate. Subsequent items will ask how PSC services may support people with Inflammatory arthritis to live well, and in what circumstances (e.g. symptom profile, stage of disease, stage of life). We anticipate the survey will be "live" for 60 days and take up to 15 minutes to complete. To protect participant anonymity, IP addresses and location data will not be collected. Respondents will be invited to add their email address if they wish to contribute to Stakeholder Focus Groups (WP3). This identifiable information will be shared with the research team at DHHC and this transfer of information between UWE and DHHC will be made explicit in the PIS.

Downloaded data (quantitative and qualitative) will be analysed descriptively without between-groups comparisons or associations between variables. Content analysis will be applied to responses to open questions.

#### **4.4 WP3 (months 13-17)**

**Establish the views of expert stakeholders on 1. nature and scope of 'unmet need' as described in our data; 2. key points for Rheumatology, Palliative Care, Primary Care, and Community services future clinical practice and research; 3. barriers and facilitators to implementing this expert opinion.**

##### **4.4.1 Inclusion and exclusion criteria**

**Inclusion criteria:** Four population groups will be included in this WP who represent the key demographics best placed to have knowledge, experience and views on this topic to inform next steps.

- a) People who meet inclusion and exclusion criteria for WP1
- b) HCPs who meet inclusion/exclusion criteria for WP2
- c) Representatives from key charities and national organisations (e.g. Arthritis UK, National Rheumatoid Arthritis Society, National Axial Spondyloarthritis Society, Hospice UK).
- d) Commissioners of services in Integrated Care Boards.

**Exclusion criteria:** Unable to access Microsoft teams; non-English speaker without access to a nominated interpreter (should an interpreter not be available).

**4.4.2 Sample size:** Guest et.al. recommend three focus groups as sufficient to capture the most prevalent themes in a topic area. Due to the diversity and number of HCPs, in terms of Specialty and Setting, we will conduct four stakeholder focus groups to ensure we capture a representative breadth of views. Each group will comprise a minimum of two and maximum of four representatives from populations a) and b), and a minimum of one representative from population c). It is hoped at

least one focus group will include representation from population d) but practicalities may require 1:1 consultation with this group (n=2).

**4.4.3 Recruitment:** Participants who have volunteered in WPs1 and 2 to participate, will be contacted again to confirm interest. Email invitations will be sent to identified key charities and national organisations, and to Integrated Care Board Medical and Commissioning leads for Bristol and Bath regions.

**4.4.4. Data collection** Data from WP1 and 2 will be assimilated into a 'key findings' presentation to be shared with expert stakeholders. Pre-application rapid literature review will be repeated and any new findings included in this presentation. A summary of the project's findings, and links to the three videos used, will be sent to participants prior to the online event/s to optimise the potential for reflective and deep discussion. This summary will be used as a topic guide to steer the discussion to key questions. Focus groups will be conducted face to face (x2) and online (x2) via Microsoft Teams at a date and time convenient to participants, and following **participant consent**, recorded using embedded audio recording function. Each focus group will run for a maximum of 120 mins. Discussion will broadly focus on:

- What would 'good' look like for people with Inflammatory arthritis to live well with support from PSC services?
- How would this be measured?
- What is the current unmet need?
- What could reduce/address this unmet need in Rheumatology and Palliative care services?
- What are the challenges and barriers?
- What further clinical and/or research work is required?

After each event, the discussion will be summarised by the lead facilitator ([name] or [name]) and confirmed by members of the group. An iterative approach will be taken across these events so the final summary is representative of the discussion from all Stakeholder events. For example, in groups 2 and 3, following initial discussion and agreement of draft recommendations, the views of the previous Stakeholder group/s will be shared and added to or refined. Using transcribe function within Microsoft 365, audio data will be transcribed verbatim and analysed using inductive qualitative content analysis.

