## **5. STUDY SETTING**

The majority of this study collects data online (WP1, WP2 and 2 focus groups in WP3). The two face to face focus groups in WP3 will be conducted at Dorothy House Hospice.

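### The WP3 exclusion for lack of Microsoft Teams covers all four focus groups, although two are face to face and do not need it; Objective 3.2 still describes four online groups

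*Protocol*

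**What the plan says.** The protocol describes how the WP3 focus groups will be held in three places, and they do not agree.

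- Section 3.2 (Objectives): "Conduct four online stakeholder focus groups to agree".
- Section 4.4.4 (WP3 data collection): "Focus groups will be conducted face to face (x2) and online (x2) via Microsoft Teams".
- Section 5 (Study setting): "The two face to face focus groups in WP3 will be conducted at Dorothy House Hospice".

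Eligibility for WP3 is set in section 4.4.1. The patient population, group a), is "People who meet inclusion and exclusion criteria for WP1". The exclusions that follow apply to the work-package as a whole: "Unable to access Microsoft teams; non-English speaker without access to a nominated interpreter".

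The WP1 criteria that group a) inherits are in section 4.2.1 and ask for "access to Microsoft Teams or a telephone". Section 3.2 likewise plans to "Conduct semi-structured online or telephone interviews with people living with an inflammatory arthritis". Section 4.2.5 adds, for the WP1 interviews: "Communication via MS Teams can be via computer or telephone (without the need for a camera".

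**The concern.** A blanket Teams requirement fits a design in which every group meets online, which is what Objective 3.2 describes. It does not fit sections 4.4.4 and 5, under which half the groups meet at the hospice. No sentence limits the exclusion to the online groups or makes an exception for people attending in person.

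The patient route into WP3 makes this matter. WP1 is open to people who have only a telephone, it keeps contact details for those willing to join WP3 (section 4.2.5), and section 6.3 expects most WP3 participants to be volunteers from WP1 and WP2. A telephone-only patient can therefore satisfy inclusion a), volunteer, and then meet an exclusion that has no bearing on the meeting they would attend.

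WP3 is where the stakeholders settle the recommendations, which are among the primary outcomes in section 3.4, and section 4.4.2 justifies four groups by the wish for a broad range of views. Staff who apply the criterion as written turn away willing patients. Staff who apply it sensibly depart from approved eligibility criteria.

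**Working it through.** There is no stated figure to reproduce. The check is a comparison of texts plus a short count.

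**1. Mode of the groups.** Section 4.4.4 gives 2 face to face + 2 online = 4, which agrees with the four groups in section 4.4.2. Section 5 confirms the 2 in-person groups. Objective 3.2 gives 4 online and 0 in person. Sections 4.4.4 and 5 agree with each other, and Objective 3.2 is the outlier.

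**2. Reach of the exclusion.**

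| Group type | Groups (4.4.4, 5) | Is Teams needed to attend? | Does the 4.4.1 exclusion apply? |
|---|---|---|---|
| Online | 2 | Yes | Yes |
| Face to face | 2 | No | Yes |

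The exclusion has an operational purpose in 2 of 4 groups and none in the other 2. Section 4.4.4 also mentions an embedded audio recording function without separating the group types. That concerns how the team records the session and does not require an attendee in the room to have Teams.

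**3. Who is caught.** Sections 3.2 and 4.2.1 list online or Teams access and the telephone as alternatives, so a person with a telephone and no Teams is eligible for WP1 and hence for WP3 population a). Section 4.2.5 says that Teams can itself be reached by telephone, but only for WP1. There are then two cases in WP3:

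- If dial-in counts as Teams access, the exclusion catches only people with no Teams route at all, by computer or by telephone.
- If dial-in does not count, it catches every telephone-only volunteer.

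The protocol does not say which case applies in WP3. In both, the requirement serves no purpose for an in-person meeting.

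**4. Places concerned.** Section 4.4.2 sets two to four representatives per group from populations a) and b). If that range applies to patients alone, the two in-person groups hold 2 × 2 = 4 to 2 × 4 = 8 patient places, out of 4 × 2 = 8 to 4 × 4 = 16 overall. If it covers patients and healthcare professionals together, there are fewer patient places. These are places, not people lost.

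**5. People concerned.** The number turned away is the number of WP1 interviewees, times the share with no Teams route, times the share of those who volunteer for WP3, times the share of those who could attend in person. Section 6.1 gives a rate of at least 6 a month for four months, 6 × 4 = 24 interviewees. None of the three shares is given or can be derived, and any of them may be zero. No useful estimate follows.

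**The case against.** The strongest reply is that a telephone is one way of reaching Teams in this protocol. Section 4.2.5 conducts the WP1 interviews on Teams, allows participants to join by telephone, and offers guidance on using Teams. On that view few people, perhaps none, are unable to access it. This stands as a limit on the number affected. It does not remove the inconsistency: the sentence is not repeated for WP3, sections 3.2 and 4.2.1 treat the two routes as alternatives, and the Teams condition still covers in-person meetings.

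Three stronger readings are tempting, and the documents do not support them.

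- A reader might infer that every telephone-only patient is barred from WP3. Section 4.2.5 leaves that open, as shown above.
- A reader might assume a telephone-only share, apply it to about 24 interviewees, and report a count of lost volunteers. That assumes that all interviewees volunteer and can travel. The in-person groups are at one hospice, whereas section 4.2.3 recruits through a national hospice network and national research networks.
- A reader might call this selection bias in the primary outcomes. The study is exploratory, WP1 is purposive and self-selecting, and WP3 estimates no quantity. Patients interviewed by telephone contribute fully to WP1, and the key-findings summary carries those data into the WP3 discussion. Section 6.3 also allows further recruitment if volunteers are short, so the group minimums are not shown to be at risk.

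The interpreter half of the quoted criterion is not part of this point. Population a) inherits the WP1 criteria, which already allow a nominated or agency interpreter, and the WP3 exclusion is qualified by whether an interpreter is available.

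**Conclusion.** The concern holds as an eligibility criterion that contradicts the delivery plan. The Teams exclusion covers 4 groups where 2 need it, and Objective 3.2 conflicts with sections 4.4.4 and 5 on how the groups are held. Read literally, a patient eligible for WP1 by telephone who cannot reach Teams is barred from the in-person groups as well, which narrows direct patient input to the recommendations without a stated or evident reason.

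The importance is moderate. The number of patients affected is unknown and may be small, and no analysis or sample target is shown to fail. The conclusion rests only on the text: that the section 4.4.1 exclusion is unconditional, and that sections 4.4.4 and 5 give the intended design. If Objective 3.2 were the intended design, the exclusion would be consistent and sections 4.4.4 and 5 would need changing instead.

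**What to change.** Make three small wording changes.

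1. Section 4.4.1: limit the criterion, for example *unable to access Microsoft Teams (online groups only)*.
2. Section 4.4.1 or 4.4.4: state that joining by telephone dial-in counts as Teams access for the online groups, as it does in WP1.
3. Section 3.2: change the objective to *four stakeholder focus groups (two face to face, two online)*.

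The cost is drafting plus whatever amendment review section 7.2 requires. The number of groups, the sample size and the analysis do not change. WP3 is scheduled for months 13 to 17, and section 7.2 does not allow an amendment to be implemented before approval, so the change should be made before WP3 invitations are sent.

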#### **4.5.3 WP3 Stakeholder Focus Groups**

Transcribed data will be uploaded onto NVivo, and analysed by RF, supported by project lead [name], using inductive qualitative content analysis in a three-phase process.

1. Preparation phase: collecting suitable data, making sense of the data and selecting the unit of analysis. Each focus group transcript will be considered a single 'unit of analysis' as large enough to be considered whole but small enough to be kept in mind during the analysis process. Transcribed text will be categorised into content areas (approximately 6), or NVivo 'parent nodes', that reflect the questions asked in the stakeholder focus groups.
2. Organisation phase: open coding, creating categories and abstraction. Headings will be attributed to the text, and categories freely generated (open coding). Categories will be compared and grouped into higher order categories, where text appears to 'belong together'. During abstraction, categories will be re-compared and re-grouped and put into a hierarchical model of closeness to distance from the text.
3. Reporting phase: The content of the categories will be described and reported in detail to our Public Contributors and the research team to

increase trustworthiness of findings, prior to publication. The findings will be presented as clinical and research recommendations for PSC, to help people with inflammatory arthritis to live well over the course of their disease. We will particularly consider Supportive Care, within the 'six pillars' framework, as this includes improving a person's general physical and mental health..

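### The WP3 discussion questions are narrower than the WP3 aims: the solution question names two of the four services, and no question names facilitators

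*Protocol*

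**What the plan says.** Protocol section 4.4 gives WP3 three aims. The first is the nature and scope of unmet need. The second is "key points for Rheumatology, Palliative Care, Primary Care, and Community services future clinical practice and research". The third is "barriers and facilitators to implementing this expert opinion".

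Section 4.4.4 then lists six questions, introduced by "Discussion will broadly focus on". In short form they are: (1) what good would look like, (2) how it would be measured, (3) the current unmet need, (4) "What could reduce/address this unmet need in Rheumatology and Palliative care services", (5) "What are the challenges and barriers", and (6) "What further clinical and/or research work is required". The same section says of the pre-circulated findings summary: "This summary will be used as a topic guide to steer the discussion to key questions".

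Section 4.5.3 sorts the transcripts into approximately six content areas, or NVivo parent nodes, "that reflect the questions asked in the stakeholder focus groups". Open coding follows within an inductive content analysis.

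**The concern.** The aims and the questions are both fixed in the protocol, and they differ in two places. Aim 2 covers four services, while the one question on how to address unmet need names two. Aim 3 has two halves, while the one question on implementation names only the first.

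The service mismatch is more than loose phrasing. A question that named no service would leave the field open. One that names Rheumatology and Palliative Care points the discussion at those two, at the moment when solutions are being sought. The protocol's own rationale runs the other way. Section 1 reports that general practitioners and community professionals asked to be included and would welcome guidance, and sections 3.2 and 3.3 name both services.

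What is at stake is interpretation. If the groups say little about Primary Care or Community services, a reader could not easily tell whether there was little to say or whether the question did not invite it. Section 3.4 also foresees later work on implementing the recommendations, and knowledge of facilitators would serve that work.

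**Working it through.** No formula applies, so the check is a count and a side-by-side reading.

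**The plan's own figure.** Section 4.5.3 gives approximately six parent nodes. Section 4.4.4 lists six questions. The two agree, which supports reading the nodes as roughly one per question.

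**Aims in 4.4 against questions in 4.4.4.**

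| Element of the WP3 aims | Closest question | Match |
|---|---|---|
| Unmet need | 3 | Full |
| Key points, Rheumatology | 4 and 6 | Named in 4 |
| Key points, Palliative Care | 4 and 6 | Named in 4 |
| Key points, Primary Care | 6 | Not named; 6 is open to it, 4 is not |
| Key points, Community services | 6 | Not named; 6 is open to it, 4 is not |
| Barriers | 5 | Named |
| Facilitators | None | Not named; 4 may draw them out indirectly |

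**Counts.**
- Services named in the solution question: 2 of 4.
- Halves of aim 3 named in any question: 1 of 2.
- Questions with no limit by service: 6 − 1 = 5 (questions 1, 2, 3, 5 and 6).

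**Carry-through to the analysis.** If each parent node mirrors a question as written, the solutions node takes on the two-service frame and the implementation node is one of challenges and barriers. Neither Primary Care and Community solutions nor facilitators then has a dedicated parent node. Categories below that level are generated freely, so such material can still be coded if participants raise it.

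**Does group composition close the gap?** Population b) in 4.4.1 takes in everyone eligible for WP2, which under 4.3.1 includes GPs, district nurses and therapists. Section 4.4.2 sets a minimum and a maximum for representatives of populations a) and b), but no minimum by specialty or setting. A given group may therefore include Primary Care or Community staff, but need not.

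**The case against.** The strongest reply is that the list is indicative. Discussion is only to focus broadly on it, and the findings summary is the topic guide. That summary draws on WP2, which surveys GPs and community teams, so their concerns can reach the groups by that route. Five of the six questions carry no service limit, and question 6 is close to aim 2 in content. Members confirm the summary of each group, and later groups can add to or refine the recommendations. Section 4.4.2 adds a fourth group because of the diversity of professionals.

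Most of this stands, and it rules out several stronger readings that a reader might infer.

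- *That Primary Care and Community services have no prompt at all.* Question 6 and the four other unrestricted questions admit them.
- *That there is no coding category for this material or for facilitators.* Open coding can create one. Only a dedicated parent node is absent.
- *That part of a primary outcome goes uncollected.* Section 3.4 lists the recommendations as a primary outcome but names neither the four services nor facilitators. Facilitators are a WP3 aim only.
- *That sparse Primary Care or Community recommendations would be produced by the question wording.* That supposes that moderators read the list literally and do not probe, which the protocol does not say.

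The reply does not show that the questions match the aims. It shows that the missing content may surface anyway. Sharing earlier groups' views with later ones also works both ways: it can correct an omission, or it can pass on a starting point that already has one. No part of the reply supplies an explicit prompt for facilitators.

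**Conclusion.** The mismatch is real and limited. The only solution question names two of the four services that aim 2 requires. No question names facilitators, which are half of aim 3. The parent nodes follow the questions. Primary Care and Community content is therefore not explicitly prompted where solutions are sought, facilitators are not explicitly prompted anywhere, and neither has a dedicated parent node.

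No sample size or numerical result is affected. The conclusion rests on two assumptions: that the listed questions are used substantially as written, and that the parent nodes correspond to them roughly one to one. If moderators probe more widely, or a further node is added, which the word approximately allows, the practical effect shrinks. The texts would still need aligning. It is worth doing because the protocol itself fixes both the aims and the questions, the question as worded steers away from two services that the aim includes, and the correction costs almost nothing before WP3 begins.

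**What to change.** In 4.4.4, name Rheumatology, Palliative Care, Primary Care and Community services in the fourth question, or remove the service restriction from it. Change the fifth question so that it asks about both barriers to, and facilitators of, putting the recommendations into practice. In 4.5.3, let the parent nodes follow the revised questions.

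The cost is a rewording of two questions before WP3 starts, and slightly more discussion to fit within the 120-minute limit. No extra participants or groups are needed. Taking the four services in turn and reporting recommendations by service are optional; aim 2 requires neither, and some groups may lack a representative of a given service.
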